5.3.2. Caffeine, Alcohol, and Tobacco

- Participants will abstain from caffeine-containing products for 24 hours prior to the start of dosing and during confinement in the CRU.
- Participants will abstain from alcohol for 24 hours prior to admission to the CRU and continue abstaining from alcohol until collection of the final PK sample. Participants may undergo an alcohol breath test or blood alcohol test at the discretion of the investigator.
- Participants will abstain from the use of tobacco- or nicotine-containing products for 24 hours prior to dosing and during confinement in the CRU.

5.3.3. Activity

- Showering/Bathing: Participant's dosing areas of skin are required to be dry for at least 30 minutes prior to each study drug application. To help facilitate this, participants will not be permitted to shower or bathe within 1 hour prior to and 4 hours after any study drug dose application. Participants are not required to shower or bathe prior to each dose application. If participants choose to shower or bathe, it will occur at least 1 hour prior to the AM and PM dose.
- Participant should not use any products in the area where the investigational product is applied during confinement in the CRU.
- Participants should be encouraged not to touch the area of application.
- Participants should be encouraged not to put hands in the mouth to avoid ingestion of investigational product.
- Participants should avoid wiping the investigational product off the skin.
- Participants will abstain from strenuous exercise (eg, heavy lifting, weight training, calisthenics, aerobics) for at least 48 hours prior to each blood collection for clinical laboratory tests. Walking at a normal pace will be permitted.
- Participants are permitted to participate in light recreational activities during the study (eg, watching television, reading). Following application, study participants are required to wear loose-fitting clothing and avoid activity for at least 4 hours post AM and PM dose, to minimize the study medication being wiped off the skin or the treated areas to become occluded.

5.3.4. Contraception

The investigator or his or her designee, in consultation with the participant, will confirm that the participant has selected an appropriate method of contraception for the individual participant and his or her partner(s) from the permitted list of contraception methods (see Appendix 4 Section 10.4) and will confirm that the participant has been instructed in its consistent and correct use. At time points indicated in the schedule of activities (SoA), the investigator or designee will inform the participant of the need to use highly effective contraception consistently and correctly and document the conversation and the participant's affirmation in the participant's chart (participants need to affirm their consistent and correct use of at least 1 of the selected methods of contraception) considering that their risk for pregnancy may have changed since the last visit. In addition, the investigator or designee will instruct the participant to call immediately if the selected contraception method is discontinued or if pregnancy is known or suspected in the participant or partner.

5.4. Screen Failures

Screen failures are defined as participants who consent to participate in the clinical study but are not subsequently entered in the study. Screen failure data are collected and remain as source and are not reported to the clinical database. Individuals who do not meet the criteria for participation in this study (screen failure) may be rescreened and enrolled in a subsequent group or cohort.

6. STUDY INTERVENTION(S) AND CONCOMITANT THERAPY

Study intervention is defined as any investigational intervention(s), marketed product(s), placebo, medical device(s), or study procedure(s) intended to be administered to a study participant according to the study protocol.

For the purposes of this protocol, the term investigational product may be used synonymously with study intervention.

6.1. Study Intervention(s) Administered

For this study, the investigational products are PF-07295324 (0.12%), ointment and PF-07259955 (2%), cream, as well as the corresponding vehicles for each IP.

Both the IPs (PF-07295324 and PF-07259955) and vehicles (ointment and cream) will be supplied by Pfizer to the CRU as packaged 60 gram tubes and labeled according to local regulatory requirements in an unblinded fashion.

Both the IPs (PF-07295324 and PF-07259955) and vehicle doses will be prepared by the unblinded CRU pharmacist and provided to the blinded investigational site staff.

During the stay in the CRU, study drug applications will be performed by trained study staff to ensure proper study drug application.

6.1.1. Administration

6.1.1.1. PF-07295324 and PF-07259955 Administration

The IP will be applied in blinded fashion, at the CRU. All applications of the IP will be dispensed and applied by study site staff from D1 AM through D10 AM dose. For Cohort 1 and Cohort 2, topical formulation will be applied Q12H on D1-D9 to the area identified on D-1 or D1. Only the AM dose will be applied on D10. Every effort must be made for the AM applications on D2 to D10 to be completed approximately 24±2 hour intervals from the recorded time of completion of the D1 dose application, for each participant. The PM dose application on D1 through D9 will be applied approximately 12±1 hour after the recorded time of completion of the AM dose application, for each participant.

For optional Cohort 3 and Cohort 4, formulation may be of a lower strength or equal to that of the planned cohort; administration procedures will be similar to that of planned cohorts. If study intervention in the optional cohort/s is once daily, formulation will be applied at AM only, from D1 to D10.

The per application dose will be calculated using the formula provided below in Section 6.1.1.2. The intended application rate is approximately 2.5 or 2 mg/cm^2 for PF-07295324 or PF-07259955, respectively. The IP should be applied evenly to all pre-specified areas. The per application dose will be expressed as the weight of ointment or cream in grams. The per application dose will remain fixed and the IP will be applied to the areas identified on Day 1.

In order to standardize the conditions on PK sampling days, all participants will be required to refrain from lying down for at least 4 hours post application (except when required for BP, pulse rate, and ECG measurements).

6.1.1.2. Calculation of Per Application Dose

The per application dose (expressed in g) will be calculated by study site staff, for each participant, using the formula below:

BSA \times Application rate (g/cm²) = Weight of investigational product (in g) per application.

where BSA is less than or equal to 4000 cm^2 () and application rate is 2.5 mg/cm² (for cohorts assigned to PF-07295324/vehicle) and 2 mg/cm² (for cohorts assigned to PF-07259955/vehicle).

6.1.1.3. Application of Investigational Product

Before the D1 AM dose is applied for each participant, the designated areas for treatment will be identified on D-1 or D1 and documented in the participants' study records. The treatment areas will be mapped using surgical markers (on D-1 or D1) to outline areas to ensure they remain the same throughout the double-blind treatment period. For each subsequent investigational product application, study site staff will refer to the documented locations as determined on D-1 or D1.

To standardize the application, the investigational products will be applied to a BSA of approximately 20% ($\pm 10\%$) or less than or equal to 4000 cm² ± 400 , for 10 consecutive days, at an approximate formulation rate of 2.5 mg/cm² or 2 mg/cm² for PF-07295324 or PF-07259955, respectively.

For participants in Cohort 1 and Cohort 2, the application area will include the back as well as other extremities identified by the investigator.

For participants in optional Cohort 3 and Cohort 4, if study intervention is planned for lower body surface areas, smaller treatment area may be mapped for topical administration.

Wearing gloves, study site staff will apply the formulation to the areas determined on D-1 or D1. Study drug will be applied as a thin layer on participants' skin. Care must be taken to avoid study drug contamination of designated venous access areas used for PK sampling, by leaving an untreated margin of at least 5 cm radius around each venipuncture site. Following investigational product application, participants will be instructed to wear loose fitting clothing, to not wipe investigational product off the skin, and to refrain from bathing, sauna or washing the treated areas within 4 hours after application. At 4 hours postdose, investigational product will be wiped from all application sites, with a clean towel.

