4.3.1. Dose rationale for PF-07295324

Solubility and chemical stability of PF-07295324 with topical excipients were key drivers to nominate the maximal strength ointment formulation of 0.12% (w/w).

The PF-07295324 formulation when applied to human skin (stimulated ex-vivo), caused dose-dependent inhibition of gene expression of pro-inflammatory molecules CXCL10, CCL26 and MMP12 stimulation of gene expression of filaggrin, a protective skin barrier protein. Maximum effects were observed at the formulation strength proposed in this study. (IB Section 5.1.2.1.4. and summarized in protocol Section 2.2.1).

Steady state systemic exposures following topical administration of PF-07295324 (0.12%), once daily or Q12H, on approximately 20% BSA, have been projected assuming ointment application rate of approximately 2.5 mg/cm², dermal availability of approximately 10%, (similar to that estimated in minipigs at steady-state, following topical administration of 0.12% PF-07295324 ointment, BID) and predicted human hepatic clearance of 7.4 mL/min/kg (Section 2.2.2.1). The projected steady-state systemic exposures following topical administration of 0.12% PF-07295324, are summarized in Table 3.

Table 3.Projected steady-state exposures and Safety Margins Following
Administration of Multiple Topical Doses of PF-07295324 (0.12%), once daily
or twice daily on 10-20% BSA, in Healthy Adult Participants

СОН.	FORM. STRENGTH (%)	QD/ BID	%BSA	TDD ^a (mg)	DOSE SYS. ^b (mg)	AUC24 ^b (ng*h/mL)	uCavg (ng/mL)	uCavg.IFN y °	uCAVG.SM ^d
Coh. 1	0.12	BID	20	24	2.4	77	0.48	18	183
Optional	0.12	BID	10	12	1.2	39	0.24	35	367
Coh. 3									
Optional	0.12	QD	20	12	1.2	39	0.24	35	367
Čoh. 3									

a. Total daily dose calculated as appropriate for once daily or twice daily application and as a product of formulation strength and body surface area, assuming an ointment application rate of approximately 2.5 mg/cm².

b. Assuming median healthy participants BW ~70 kg, unbound exposures were predicted using $CL_p=30.8$ L/h, $V_d=56$ L, Fa.Fg=1, F=0.1, and in vitro fraction unbound in human plasma $f_{u,p}=0.148$; MW = 467.5; 1 ng/mL unbound PF-07295324 is equivalent to 2.08 nM.

c. Multiples have been calculated relative to PF-07295324 unbound plasma IFN γ IC₅₀ of 18 nM.

d. Margins have been calculated relative to PF-07295324 NOAEL unbound C_{avg}=88 ng/mL in 6 week oral GLP toxicology study in rat; systemic safety margins have been calculated based on unbound plasma exposures.

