As summarized in Table 3, following topical administration of maximum feasible formulation (0.12%) of PF-07295324, Q12H, on approximately 20% BSA the projected steady-state average unbound plasma concentration (C_{avg}) is 0.48 ng/mL.

Based on the projected steady-state systemic exposure [0.48 ng/mL (1 nM) is ~18-fold below the unbound IFN γ IC₅₀ (18 nM)] following topical administration of PF-07295324 (0.12%, Q12H, 20%BSA).

This highest projected average unbound exposure is approximately 183-x below the rat unbound NOAEL C_{avg} of 88 ng/mL. In minipigs, topical administration of an equivalent dose resulted in minimal, non-adverse local irritation (Section 2.2.3.1). The NOAEL in the PF-07295324 pivotal 6-week dermal toxicity study in minipigs was 0.0528 mg/cm2/day, resulting in an ~8.8-x dose margin based on an anticipated clinical application rate of 2.5 mg/cm² and dose of 0.006 mg/cm²/day (0.12% ointment, BID).

Overall, multiple topical administrations of PF-07295324 (0.12%), in healthy adult participants is expected to be safe and well tolerated, locally and systemically.

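### PK blood may be drawn from a treated limb, because the 5 cm bare margin guards against surface contamination but not against drug draining from treated skin upstream of the sampled vein

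*Protocol*

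**What the plan says.** In Cohorts 1 and 2, Protocol Section 6.1.1.3 says "the application area will include the back as well as other extremities identified by the investigator". Arms are neither named nor excluded. The mapped areas are entered in the study records and stay the same throughout dosing.

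The same section gives the only rule on where PK blood is drawn: "Care must be taken to avoid study drug contamination of designated venous access areas used for PK sampling", to be achieved "by leaving an untreated margin of at least 5 cm radius around each venipuncture site". The stated aim is to avoid contamination. Venous drainage from treated skin is not mentioned.

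Other relevant places:

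- Protocol Section 8.4 requires the date and time of each PK sample, but not the limb or site. Collection instructions are left to the laboratory manual or the sponsor.
- The opening of Protocol Section 8 allows an IV catheter but does not say where it is placed.
- SAP Section 4.2 lets the pharmacokineticist exclude a concentration judged anomalous. SAP Section 5.3 sets such values to missing in summaries and drops PK parameter estimates known to be biased. Neither section has a rule for samples from a treated limb.

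**The concern.** The secondary endpoints describe systemic plasma PK. Blood from a vein that drains treated skin carries the systemic concentration plus a local contribution that has not yet been diluted in the circulation. A bare circle at the needle does not remove that contribution when treated skin lies further out on the same limb.

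The result would depend on which limb was treated and which was sampled in each participant. Each cohort has about 4 active participants, so one or two affected profiles could move the mean and widen the spread. Concentrations and AUCs would be pushed up, and CL/F and Vz/F down. Rac compares Day 10 with the first dose. It could be pushed either way if a treated arm is sampled on one of those days and an untreated arm on the other. These summaries would be set against the exposures projected in Protocol Section 4.3, and SAP Section 7.2 allows PK data to be reviewed while the study is running.

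**Working it through.** **1. Reproduce the projected exposures** (Protocol Sections 4.3.1, 4.3.2 and 6.1.1.2; Tables 3 and 4).

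The area is capped at 4000 cm² ("where BSA is less than or equal to 4000 cm^2"). Clearance for PF-07295324 comes from a "predicted human hepatic clearance of 7.4 mL/min/kg": 7.4 × 70 kg × 60/1000 = 31.1 L/h, and Table 3 uses 30.8. For PF-07259955, 6.1 × 70 × 60/1000 = 25.6 L/h, and Table 4 uses 26.

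Unbound Cavg = area × rate × strength × 2 × F ÷ CL ÷ 24 × fu.

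| Step | PF-07295324 | PF-07259955 |
|---|---|---|
| Daily dose | 4000 × 2.5 × 0.0012 × 2 = 24 mg | 4000 × 2 × 0.02 × 2 = 320 mg |
| Absorbed | × 0.10 = 2.4 mg | × 0.087 = 27.8 mg |
| AUC24 | ÷ 30.8 L/h = 77.9 ng·h/mL (stated 77) | ÷ 26 L/h = 1071 (stated 1100) |
| Total Cavg | ÷ 24 = 3.25 ng/mL | ÷ 24 = 44.6 (stated 45) |
| Unbound Cavg | × 0.148 = 0.48 (stated 0.48) | × 0.345 = 15.4 (stated 16) |

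The first agrees with the protocol's statement that "the projected steady-state average unbound plasma concentration (C_{avg}) is 0.48 ng/mL". The second agrees within rounding (15.8 if AUC24 is first rounded to 1100).

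**2. What the margin covers.** A circle of 5 cm radius is π × 25 = 78.5 cm², about 2% of 4000 cm². Treated skin beyond the circle and distal to the site can still drain into the sampled vein.

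**3. Relative excess.** Let R be the total absorption rate. At steady state the systemic concentration is R/CL. If a share f of R enters upstream of the sampled vein and regional flow is Q, the local addition is f × R/Q. Therefore:

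excess ÷ systemic = f × CL/Q

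Dose and F cancel. Neither f nor Q is in the documents, so both are assumed. Blood and plasma concentrations are taken as equal. Protocol Section 2.2.2 says both drugs favour plasma over blood cells in humans, so for a given blood flow this simplification does not inflate the result.

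| Assumed f, Q | CL = 30.8 L/h | CL = 26 L/h |
|---|---|---|
| 0.05, 6 L/h | 0.05 × 30.8/6 = +26% | +22% |
| 0.10, 3 L/h | 0.10 × 30.8/3 = +103% | +87% |
| 0.20, 1.8 L/h | 0.20 × 30.8/1.8 = +342% | +289% |

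With f from 0.01 to 0.15 and Q from 0.5 to 5 L/h, the ratio of sampled to systemic concentration runs from 1.06 to 10.2 for PF-07295324 and from 1.05 to 8.8 for PF-07259955. With f = 0 it is exactly 1.

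The formula describes the steady-state average. It does not give a size for the Day 1 profile.

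**4. Effect on a cohort of 4 active participants.** Take equal true exposures and one participant at the middle case (+103%). The mean becomes (3 + 2.03)/4 = 1.26 times the truth. The SD goes from 0 to 1.03/√4 = 0.515, a CV of 0.515/1.26 = 41%.

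**5. Effect on the margins.** At the largest values in the table, the 183-fold margin would appear as 183/4.42 = 41-fold and the 110-fold margin as 110/3.89 = 28-fold. At the middle case, the 3.7-fold distance of PF-07259955 from its IFNγ IC50 would appear as 3.7/1.87 = 2.0-fold. All of these understate the true distance.

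**The case against.** The strongest reply is that the trigger may never occur. The protocol does not say that arms will be treated, and a site that maps the back and legs would meet Section 6.1.1.3 and have no problem. The 5 cm rule may only be a precaution about nearby skin. The laboratory manual is not among the documents and may already fix the draw site. All of this stands, so the point is conditional. What remains is that a site following the protocol exactly may treat and sample the same arm.

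The second reply is that the size is unknown. That also stands. Assumed inputs that give anything from about 5% to about tenfold do not establish an effect, and f = 0.20 would need about 800 cm² of treated skin (0.20 × 4000), all upstream of one vein. A reader might take the percentages as an expected bias. The documents do not support that.

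Third, a reader might infer that nothing in the analysis could remove the error. That is too strong. Individual profiles are listed and plotted, medians are reported, and anomalous concentrations can be excluded (SAP Sections 4.2, 5.3 and 6.2.1). A gross outlier could be caught. A modest shift probably would not, and the rule on known biased estimates cannot be applied to a bias that nobody can trace to the sampled limb.

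Fourth, a reader might infer a threat to the safety margins. The error overstates exposure, so it is conservative there. No dose escalation is planned, and the PK analysis is secondary and descriptive.

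**Conclusion.** The concern holds in conditional form. As written, the protocol allows PK blood to be drawn from a treated arm, and its only safeguard addresses a different problem. If that happens, concentration and AUC summaries are biased upward, CL/F and Vz/F downward, and Rac may be distorted when the sampled arm changes between days. The direction follows from mass balance. The size depends on f and Q, which the documents do not give: about +20% to +340% over one assumed range, wider over another, and zero if the sampled limb is untreated. The documents do not show that the bias will occur, and they do not support a single figure for it.

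This is a cheap improvement to the secondary PK endpoints, not a safety defect. It is worth making before sampling starts, because without a record of the sampled limb a modest bias cannot be recognised afterwards.

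**What to change.** - In Protocol Section 6.1.1.3, state that PK samples are drawn from a limb that has received no investigational product, and align the laboratory manual with this.
- Keep the 5 cm margin as a precaution against surface contamination.
- Record the sampled limb in the CRF for each PK sample. Treated areas are already documented, so this is the missing item. It would also let the existing SAP rules on anomalous concentrations and biased parameters be applied to any sample taken from a treated limb.

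The cost is slightly less freedom in mapping the treated area, plus repeated draws on the spared arm. There are about 19 scheduled PK samples if only one arm is spared: 8 from 0 to 24 h after the Day 1 dose, one each on Days 5 and 7, 8 from 0 to 24 h on Day 10, and one on Day 12. No samples or visits are added. The sponsor should confirm that the intended area can still be mapped with a limb left free.

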6.2. Preparation, Handling, Storage, and Accountability

- 1. The investigator or designee must confirm appropriate temperature conditions have been maintained during transit for all study interventions received and any discrepancies are reported and resolved before use of the study intervention.
- 2. Only participants enrolled in the study may receive study intervention and only authorized site staff may supply or administer study intervention. All study interventions must be stored in a secure, environmentally controlled, and monitored (manual or automated recording) area in accordance with the labeled storage conditions with access limited to the investigator and authorized site staff. At a minimum, daily minimum and maximum temperatures for all site storage locations must be documented and available upon request. Data for nonworking days must indicate the minimum and maximum temperatures since previously documented for all site storage locations upon return to business.
- 3. Any excursions from the study intervention label storage conditions should be reported to Pfizer upon discovery along with any actions taken. The site should actively pursue options for returning the study intervention to the storage conditions described in the labeling, as soon as possible. Once an excursion is identified, the study intervention must be quarantined and not used until Pfizer provides permission to use the study intervention. Specific details regarding the definition of an excursion and information the site should report for each excursion will be provided to the site in the IP manual.
- 4. Any storage conditions stated in the SRSD will be superseded by the storage conditions stated on the label.
- 5. Study interventions should be stored in their original containers and in accordance with the labels.
- 6. The investigator, institution, or the head of the medical institution (where applicable) is responsible for study intervention accountability, reconciliation, and record maintenance (ie, receipt, reconciliation, and final disposition records), such as the IPAL or sponsor-approved equivalent. All study interventions will be accounted for using a study intervention accountability form/record.

7. Further guidance and information for the final disposition of unused study interventions are provided in the IP manual. All destruction must be adequately documented. If destruction is authorized to take place at the investigator site, the investigator must ensure that the materials are destroyed in compliance with applicable environmental regulations, institutional policy, and any special instructions provided by Pfizer.

Upon identification of a product complaint, notify the sponsor within 1 business day of discovery as described in the IP manual.

6.2.1. Preparation and Dispensing

Within this protocol, preparation refers to the investigator site activities performed to make the study intervention ready for administration or dispensing to the participant by qualified staff. Dispensing is defined as the provision of study intervention, concomitant treatments, and accompanying information by qualified staff member(s) to a healthcare provider, participant in accordance with this protocol. Local health authority regulations or investigator site guidelines may use alternative terms for these activities.

Prior to application, the per application dose will be carefully weighed out by CRU pharmacy staff. All study drug accountability will be recorded on the Investigational Product Accountability Log (IPAL).

PF-07295324 and PF-07259955 will be prepared by qualified unblinded site pharmacist according to the IP manual. Blinded investigational product will be applied to the participant.

